10.2 Notes on Adverse Event Inclusions and Exclusions

10.2.1 Include

- An exacerbation of a pre-existing illness
- An increase in frequency or intensity of a pre-existing episodic event/condition
- A condition (even though it may have been present prior to the start of the trial) detected after trial drug administration
- Continuous persistent disease or symptoms present at baseline that worsens following the administration of the study/trial treatment
- Laboratory abnormalities that require clinical intervention or further investigation (unless they are associated with an already reported clinical event).
- Abnormalities in physiological testing or physical examination that require further investigation or clinical intervention
- Injury or accidents

10.2.2 Do Not Include

- Medical or surgical procedures- the condition which leads to the procedure is the adverse event
- Pre-existing disease or conditions present before treatment that do not worsen
- Situations where an untoward medical occurrence has occurred e.g. cosmetic elective surgery
- Overdose of medication without signs or symptoms
- The disease being treated or associated symptoms/signs unless more severe than expected for the patient's condition

10.2.3 Reporting of Pregnancy

Females of childbearing potential will be tested for pregnancy as part of the trial screening visit and baseline visit. Any pregnancy that occurs (including any male participant that has a partner that becomes pregnant) during the study should be reported using a pregnancy CRFto the CTRC within 24 hours of the site becoming aware of its occurrence and the participant should be instructed immediately to stop taking the study drug. All pregnancies that occur during treatment need to be followed up until after the outcome using the pregnancy CRF. Consent to report information regarding these pregnancy outcomes should be obtained from the mother prior to completion and faxing of the pregnancy CRF. Any SAE experienced during pregnancy must be reported on the SAE form as appropriate (section 10.1).

The investigator should contact the participant to discuss the risks of continuing with the pregnancy and the possible effect to the foetus. Appropriate Obstetric care should be arranged.

The CTRC will report all pregnancies to the trial Sponsor. Any pregnancies that results in complication will be reported to the MHRA (UK sites) or HPRA (Dublin site).

Data on the patient and the outcome of the pregnancy must be collected. This data will be entered in the annual Developmental Safety Update Reports and the final Clinical Study Report.

10.3 Notes Severity / Grading of Adverse Events

The assignment of the severity/grading should be made by the investigator responsible for the care of the participant using the definitions below.

Regardless of the classification of an AE as serious or not, its severity must be assessed according to medical criteria alone using the following categories:

Mild: does not interfere with routine activities **Moderate**: interferes with routine activities **Severe**: impossible to perform routine activities

A distinction is drawn between serious and severe AEs. Severity is a measure of intensity (see above) whereas seriousness is defined using the criteria in section 10.1, hence, a severe AE need not necessarily be a Serious Adverse Event.

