2.3 Objectives

The main aim of this RCT is to assess the safety and efficacy (during therapy and to examine disease remission (time to first significant flare) after treatment cessation) of MTX versus CyA in severe recalcitrant atopic eczema in children.

In addition, we will examine the effect of both drugs on novel systemic and cutaneous markers of inflammation during treatment and after treatment cessation. Drug metabolites of MTX and trough levels of CyA will be measured throughout treatment to see whether they are able to predict treatment response and tolerability. Furthermore, filaggrin (FLG) genotype and T cell cytokine signatures will be determined in all trial participants to see whether these impact on treatment efficacy. We will also perform a health economic evaluation, comparing the cost effectiveness of both trial interventions.

Primary objectives:

- 1. To assess the change in atopic eczema severity between baseline & 12 weeks of treatment in the two treatment arms, and
- 2. To examine disease remission (time to first significant flare) after treatment cessation in the MTX vs CyA groups.

Secondary objectives:

- 1. To examine atopic eczema severity using the EASI, IGA, o-SCORAD & POEM scores between 0 and 12, 36, 48, 60 weeks,
- 2. To compare the number of flares in each study arm as well as the proportion of children who re-flared after treatment cessation,
- 3. To study the impact on quality of life: change in CDLQI/IDQOL & DFI scores between 0, 12, 36, 48 and 60 weeks,
- 4. To determine the proportion of participants achieving 50% improvement in the o-SCORAD and EASI index at 12, 36, 48, and 60 weeks,
- 5. To capture the proportion of participants who withdraw from treatment because of AEs,
- 6. To assess the cost-effectiveness of CyA vs MTX, based on utility measured using the CHU-9D.
- 7. To study the immuno-metabolic effects of MTX and CyA, especially in relation to markers of glycolytic activation and T cell cytokine signature, at baseline, during treatment and after treatment cessation,
- 8. To compare the drug side effects/toxicity profiles of both MTX and CyA, and
- 9. To examine the association between MTX polyglutamate and CyA trough levels and reduction in atopic eczema severity as well as drug-related side effects.
- 10. To study the impact of FLG carriage (yes/no) on reduction in atopic eczema severity.

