7.2.3 Ciclosporin - Dose Modifications

Patients should remain on the full treatment dose (4mg/kg/day for CyA) for the 12 weeks. After that, dose increases to a maximum of 5mg/kg/day or dose decreases are allowed, according to the treatment response. For decisions on treatment continuation, Pls should refer to the table below. For situations not included in the below table, this is down to the individual study centre Pl and any dose changes will be recorded in the CRF.

Table 5: Dose modification schedule

Note: any events that meet the monitoring parameters in the table below should be recorded and reported as an adverse event (see section 10.7)

Monitoring parameters	Values	Action
eGFR	Fall of >=20% (compared with eGFR value that was used to confirm eligibility)	Repeat renal profile should be done within 2 weeks of the last visit. If eGFR falls again >=20 % following repeat bloods, the trial nephrologist must be contacted to discuss potential dose reduction. If repeat bloods cannot be obtained within 2 weeks of the last visit, the trial nephrologist must be contacted within 48 hours of the site becoming aware that a repeat renal profile cannot be obtained within the timeframe (2 weeks), to discuss potential dose reduction.
Blood pressure	>95 th centile for age and sex on two consecutive visits	CyA dose adjustment, reduction by at least 20% initially and patient review. A temporary dose suspension at the PI's discretion is permitted. Repeat BP after a fortnight.
Liver function test	AST, ALT or alkaline phosphatase more than 2× upper limit of reference range	CyA dose adjustment reduction by at least 20% initially or a temporary dose suspension at the Pl's discretion. Repeat LFT weekly until normal. Further reductions in dose or stopping medication may be required but should be discussed with the Chief Investigator.
Platelet count	<100x10 ⁹ /L	CyA dose adjustment reduction by at least 20% initially or a temporary dose suspension at the PI's discretion. Repeat platelets weekly until normal. Further reductions in dose or stopping medication may be required but should be discussed with the Chief Investigator.
Neutrophil count	<1.5x10 ⁹ /L	CyA dose adjustment reduction by at least 20% initially or a temporary dose suspension at the PI's discretion. Repeat neutrophils weekly until normal. Further reductions in dose or stopping medication

		may be required but should be discussed with the Chief Investigator.

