8.3 Procedures for Assessing Safety

The following safety bloods and investigations will be performed:

- a. Safety blood profiles (full blood count, renal function and liver function) will be taken at screening, 2, 4, 8, 12, 20, 28, 36 and 60 weeks. Lipids will also be assessed at screening and week 4 as part of the safety blood profile. Safety bloods will also be taken at week 1 for the methotrexate arm. If it is not possible to obtain a safety blood sample (e.g. insufficient sample, participant refusal) at their visit, the remaining trial procedures can be carried out as normal and the patient can continue in the trial. However, the participant should be advised to temporarily stop trial treatment, until further advice is sought. The CTU should be contacted with the following information:
 - · Details of which safety blood values are missing
 - Date started treatment
 - Date and reason of any dose changes previously required
 - Details of any previous blood samples that had safety implications
 - Date of next scheduled visit

CTU will then liaise with CI (or delegate) and sponsor and will advise the site regarding the necessity to arrange an unscheduled visit to obtain missing safety assessment/s and when to reintroduce trial treatment. If a participant is not able to comply with the requested measures then permanent discontinuation of trial treatment may be considered, though in these circumstance the participant will be asked to continue in the study for follow-up purposes.

Please note, the above process does not apply to safety bloods taken at week 1 for the methotrexate arm, as this sample must be taken.

- b. BP will be taken at baseline, 2, 4, 8, 12, 20, 28, 36 and 60 weeks
- c. Chest X-Ray in those at risk of TB (discretion of local PI/medically qualified physician) at screening visit
- d. Physical examination will be carried out at each visit (except at the screening visit).

An Independent Data and Safety Monitoring Committee (IDSMC) will be constituted and will monitor adverse events and patient safety during the trial. Data on adverse events, including severity, seriousness, and expectedness as part of pharmacovigilance will be recorded at each follow-up visit and communicated to the CTRC. Requirements for pharmacovigilance reporting is detailed fully in Section 10 (Pharmacovigilance).

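### Section 10.3 grades every adverse event by interference with routine activities, so a symptomless kidney, blood-pressure, liver or blood-count abnormality is 'mild' whatever its size

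*Protocol*

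**What the plan says.** Protocol section 10.3 applies one severity scale to all adverse events, serious or not: "its severity must be assessed according to medical criteria alone using the following categories". The lowest category reads "Mild: does not interfere with routine activities". Moderate means that such activities are disturbed, and severe that they cannot be carried out. The section adds: "Severity is a measure of intensity (see above) whereas seriousness is defined using the criteria in section 10.1".

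Section 7.2.3 (Table 5, ciclosporin) states that "any events that meet the monitoring parameters in the table below should be recorded and reported as an adverse event". Section 7.3.3 (Table 8, methotrexate) has the same note. Both tables list five measured parameters: eGFR, blood pressure, liver tests, platelets and neutrophils. Section 10.2.1 also counts as adverse events "Laboratory abnormalities that require clinical intervention or further investigation".

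Section 8.3 says: "Data on adverse events, including severity, seriousness, and expectedness as part of pharmacovigilance will be recorded at each follow-up visit". Section 2.3 lists as a secondary objective: "To compare the drug side effects/toxicity profiles of both MTX and CyA".

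**The concern.** The scale has no laboratory or blood-pressure criterion, yet the protocol deliberately brings laboratory and blood-pressure findings into the set of events to be graded. Many such findings cause no symptoms when they are detected. For these, the grade is fixed by the absence of symptoms and carries no information on how far the value has moved.

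This affects the harms the protocol cares about most. Section 2.4.1 names blood pressure and kidney effects as the main concern with ciclosporin. For methotrexate it names nausea, liver abnormalities and marrow suppression. Section 2.4 calls patient safety a key secondary outcome.

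The grade goes into the record at each follow-up visit (8.3) and onto the serious adverse event form (10.7.2). Section 10.1 also defines an unexpected reaction partly by its severity. The protocol does not say that this test uses the 10.3 grade, but it offers no other severity scale.

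**Working it through.** The protocol gives no figure to reproduce here. The check has three steps.

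**Step 1. Does a symptomless measured abnormality enter the scale?** Yes. The notes to Tables 5 and 8 make any event meeting the listed values an adverse event, and 10.3 grades every adverse event.

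**Step 2. What grade results?** Under 10.3 the grade depends on one variable, interference with activities. With no symptoms, interference is nil for every value of the measurement, so the grade is constant.

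| Hypothetical symptomless event | Meets Table 5/8 | Interference | Grade under 10.3 |
|---|---|---|---|
| eGFR down 20% | yes | none | mild |
| eGFR down 60% | yes | none | mild |
| Platelets 99 ×10⁹/L | yes | none | mild |
| Platelets 30 ×10⁹/L | yes | none | mild |

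This conflicts with the same section's statement that severity measures intensity.

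**Step 3. How much of the toxicity is of this kind, and does it favour one arm?** The only counts for both drugs are those section 2.4.1 quotes from the earlier 12-week paediatric trial, with 20 children per arm. They are reports, not children, and one child may appear more than once.

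- Ciclosporin, symptoms: 2 + 1 + 3 = 6. Measured: 3 + 4 + 7 + 2 + 2 + 3 + 1 = 22. Share measured: 22/28 = 79%.
- Methotrexate, symptoms: 4 + 1 + 4 + 5 + 6 + 3 + 1 = 24. Measured: 1 + 6 + 2 + 5 + 1 = 15. Share measured: 15/39 = 38%.
- Both arms: (22 + 15)/(28 + 39) = 37/67 = 55%.

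Sensitivity to classification:

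- Anaemia and pancytopenia treated as symptomatic: ciclosporin 15/28 = 54%, methotrexate 8/39 = 21%, together 23/67 = 34%.
- Only reports matching a Table 5/8 parameter, so without anaemia and leukopenia: ciclosporin 22 − 4 − 7 = 11, methotrexate 15 − 6 − 2 = 7, together 18/67 = 27%.

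Split by organ:

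| | Ciclosporin | Methotrexate |
|---|---|---|
| Liver + kidney + blood pressure | 2 + 3 + 1 = 6 | 5 + 1 + 0 = 6 |
| Marrow | 3 + 4 + 7 + 2 = 16 | 1 + 6 + 2 = 9 |

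The arms are equal on liver, kidney and blood pressure together. The difference in measured reports comes from marrow findings, and section 2.4.1 names marrow suppression as a main methotrexate toxicity. These counts show that a substantial share of reports may be ungradable by 10.3. They do not show which arm would benefit.

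**The case against.** **No planned analysis or rule is stated to use the grade.** The safety endpoints in section 9.5 are withdrawals because of adverse events, and drug-related side effects with their association with drug levels. Dose actions in Tables 5 and 8 follow measured values. Expedited reporting follows seriousness, which includes other important medical events. The raw values are collected repeatedly, so a statistical analysis plan could analyse them whatever 10.3 says. All of this is correct and limits the consequence. It does not remove the defect: the protocol fixes the grading rule at data collection, and the grades go into visit and serious-event records before any analysis.

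**The reference to medical criteria may let the investigator look at the value.** If so, no threshold is given. The grade would then rest on site judgement by staff who know the allocation (6.4.2). That is a different weakness, not a remedy.

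**A reader might infer that the scale tilts severity comparisons towards ciclosporin, by about 4 to 1.** The documents do not support this.

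- The ratio is 24/6, the symptomatic reports in one trial. Keeping the activity scale for symptoms, or changing only how laboratory events are graded, would leave those grades as they are, so the ratio does not measure distortion due to 10.3.
- Section 2.1 describes that trial as underpowered, without an intention-to-treat analysis, and at lower than usual doses.
- The other ciclosporin trial in section 2.4.1 (42 children) found no clinically significant change in mean creatinine or blood pressure. It lists 8 + 7 + 5 + 4 + 4 + 3 + 3 + 3 = 37 clinical reports, with hyperuricaemia the only laboratory item.
- Methotrexate's liver and marrow effects are graded down by the same rule.

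**Conclusion.** The point holds as a defect of measurement. For a symptomless laboratory or blood-pressure event, the 10.3 grade is mild at any magnitude, so it cannot describe the intensity of the kidney, blood-pressure, liver and marrow harms the protocol singles out. A table by severity grade would be uninformative for those events in both arms.

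On the earlier trial's reports, 27% to 55% would be affected, depending on classification. That range assumes those findings were symptomless and that this trial's mix of events is similar. It is indicative only, given 20 children per arm and lower doses.

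A bias between arms is possible, because the drugs differ in how much of their toxicity is felt and how much is measured. Its direction and size are not established, and no claim in favour of either drug should rest on this point. The practical weight is moderate: the events are still reported, seriousness is judged separately, and the values are retained.

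**What to change.** In section 10.3, keep the routine-activities scale for symptomatic events. For events defined by a laboratory value or blood pressure, have the CTRC derive a severity category from the recorded value, for reporting only. The numeric bands should be fixed before analysis and applied without knowledge of allocation. Natural measures are multiples of the reference limit, percentage eGFR fall from the eligibility value, blood-pressure centile and cell-count bands. Report measured and symptomatic events in separate severity tables.

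This changes no dose, stopping or management rule. It costs a few lines of text, some programming and a second severity table. Scheduled values are already collected under section 8.3, so no extra visits, tests or staff are needed. The adverse event form should carry the triggering value and its date, because events found between scheduled samples, or after early discontinuation (Table 1 lists no safety bloods or blood pressure), could otherwise lack a value to band.

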10.4 Relationship to Trial Treatment

The assignment of the causality should be made by the investigator responsible for the care of the participant using the definitions in table 9.

If any doubt about the causality exists the local investigator should inform the study coordination centre who will notify the Chief Investigator. In the case of discrepant views on causality between the investigator and others, the MHRA will be informed of both points of view.

Table 10: Definitions of Causality

Relationship	Description			
Unrelated	There is no evidence of any causal relationship. N.B. An			
	alternative cause for the AE should be given			
Unlikely	There is little evidence to suggest there is a causal relationship			
	(e.g. the event did not occur within a reasonable time after			
	administration of the trial medication). There is another			
	reasonable explanation for the event (e.g. the participant's clinical			
	condition, other concomitant treatment).			
Possibly	There is some evidence to suggest a causal relationship (e.g.			
	because the event occurs within a reasonable time after			
	administration of the trial medication). However, the influence of			
	other factors may have contributed to the event (e.g. the			
	participant's clinical condition, other concomitant treatments).			
Probably	There is evidence to suggest a causal relationship and the			
	influence of other factors is unlikely.			
Almost certainly	There is clear evidence to suggest a causal relationship and other			
	possible contributing factors can be ruled out.			

10.5 Expectedness

An AE whose causal relationship to the study drug is assessed by the investigator as "possibly", "probably", or "almost certainly" is an Adverse Drug Reaction.

All events judged by the investigator to be possibly, probably, or almost certainly related to the IMP, graded as serious and **unexpected** (see SPC for list of Expected Adverse Events) should be reported as a SUSAR.

59

IRAS: 182752

10.6 Follow-up After Adverse Events

All adverse events should be followed until satisfactory resolution or until the investigator responsible for the care of the participant deems the event to be chronic or the patient to be stable.

When reporting SAEs and SUSARs the investigator responsible for the care of the participant should apply the following criteria to provide information relating to event outcomes: resolved; resolved with sequelae (specifying with additional narrative); not resolved/ongoing; ongoing at final follow-up; fatal or unknown.

10.7 Reporting Procedures

All adverse events should be reported from randomisation until 4 weeks after treatment cessation. Depending on the nature of the event the reporting procedures below should be followed. Any questions concerning adverse event reporting should be directed to the CTRC in the first instance. A flowchart is given below to aid in determining reporting requirements.

Should a trial participant be administered one of the trial treatments (ciclosporin or methotrexate) as part of routine clinical care following cessation of their trial treatment then safety reporting procedures should be followed as described here.

[figure not shown]
10.7.1 Non serious ARs/AEs

All such events, whether expected or not, should be recorded on an Adverse Event Form, which should be transmitted to the CTRC within seven days of the form being due.

10.7.2 Serious ARs/AEs/SUSARs

SARs, SAEs and SUSARs should be reported to the CTRC within 24 hours of the local site becoming aware of the event. The SAE form asks for the nature of event, date of onset, severity, corrective therapies given, outcome and causality. The responsible investigator should sign the causality of the event. Additional information should be sent within 5 days of the reaction has not resolved at the time of reporting.

The CTRC will pass on any SUSARs to Kings Health Partners Clinical Trials Office (KHP CTO) who will notify the MHRA of all SUSARs occurring during the study. The CTRC will notify the main REC of all SUSARs occurring during the study. The MHRA and main REC will be notified according to the following timelines; fatal and life-threatening within 7 days of notification and non-life threatening within 15 days. All investigators will be informed of all SUSARs occurring throughout the study. Local investigators should report any SUSARs and /or SAEs as required locally.

10.8 Responsibilities - Investigator

The Investigator is responsible for reporting all AEs that are observed or reported during the study, regardless of their relationship to study product.

All SAEs must be reported immediately (but no later than 24 hours) by the investigator to the CTRC on an SAE form unless the SAE is specified in the protocol as not requiring immediate reporting. All other adverse events should be reported on the regular progress/follow-up reports.

Minimum information required for reporting:

- Study identifier
- Study centre
- Patient number
- · A description of the event
- Date of onset
- Current status

- Whether study treatment was discontinued
- The reason why the event is classified as serious
- Investigator assessment of the association between the event and study treatment
- i. The SAE form should be completed by a designated investigator, a physician named on the 'signature list and delegation of responsibilities log' as responsible for reporting SAEs and making trial related medical decisions. The investigator should assess the SAE for the likelihood that it is a response to the investigational medicinal product. In the absence of the designated investigator the form should be completed and signed by an alternative member of the research site trial team and submitted to the CTRC. As soon as possible thereafter the responsible investigator should check the SAE form, make amendments as appropriate, sign and re-send to the CTRC. The initial report shall be followed by detailed reports as appropriate.

61

IRAS: 182752

- ii. When submitting an SAE to the CTRC research sites should also telephone the appropriate trial co-ordinator/data manager to advise that an SAE report has been submitted.
- iii. Send the SAE form by fax (within 24 hours or next working day) to the CTRC
- iv. The responsible investigator must **notify** their R&D department of the event (as per standard local governance procedures).
- v. In the case of an SAE the subject must be followed-up until clinical recovery is complete and laboratory results have returned to normal, or until the event has stabilised. Follow-up may continue after completion of protocol treatment if necessary.
- **vi.** Follow-up information is noted on another SAE form by ticking the box marked 'follow-up' and faxing to the CTRC as information becomes available. Extra, annotated information and/or copies of test results may be provided separately.
- vii. The patient **must** be identified by trial number, date of birth and initials only. The patient's name **should not** be used on any correspondence.

